### **6.2.1. Rationale for GC4419 Dose and Schedule Selection**

Data from the randomized Phase 2b study (GT-201) of GC4419 to reduce OM indicate that the acute toxicity of GC4419 at the 90 mg dose, and the overall AE profile, in combination with chemoradiotherapy will be acceptable. In addition, the efficacy results with the 90 mg dose of GC4419 in GT-201 support its use by a similar schedule and the same route and duration of IV administration in GTI-4419-203.

## **6.3. Radiation Therapy**

### **6.3.1. Radiation Therapy Dose Specifications**

1. Subjects will be scheduled to receive treatment 5 days per week, in once daily fractions, 1.8-2.0 Gy per fraction in combination with chemotherapy. Total biological equivalent dose of 120 Gy is prescribed to (PET+) gross tumor areas combined with BED>100 Gy elective target coverage where indicated.
2. All fields and the entire PTV must be treated daily. In case of machine problems or national holidays, a maximum 5-day gap and/or treatment over the weekend is permitted, additional compensating fractions are allowed per investigator discretion.
3. The assigned drug needs to be given daily **prior** to the radiation treatment for all fractions.
4. For simulation/planning GTV-PTV margins, we strongly advise 4D guidance and any form of motion management. In case 4D is not available, at least 7 mm margins are advised. Motion monitoring can reduce margins, however a minimum of 3mm CTV-PTV is recommended. Normalization of the treatment plan will cover 95% of the PTV with the prescription dose.
5. All radiation doses will be calculated with inhomogeneity corrections that consider the density differences within the irradiated volume (i.e., air in the lung and bone). Beam Energy: photons 6-18 MV are to be used. No electrons or protons are permitted. For Beam Shaping: Multi-leaf collimation (MLC) or individually-shaped custom blocks should be used to protect normal tissues outside of the target volume.
6. Re-planning and adaptive workflows are permitted, although eligibility and analyses are based on the starting treatment plan. Changes or stops in both chemotherapy and radiotherapy need to be documented.
7. The mean total dose (MTD) will be quoted as the PTV minimum target dose. This dose will be for a point that is at least 0.03 cc (approximately 3x3x3 mm) in size. The maximum and minimum point doses (within the PTV) will be reported for points that have a volume of 0.03 cc. The maximum dose must not exceed a value that is 120% of the prescribed dose. A 95% PTV coverage is aimed for.

### **6.3.2. Localization, Simulation, and Immobilization**

A volumetric treatment planning CT study will be required to define gross tumor volume (GTV), clinical target volume (CTV), and planning target volume (PTV), see definitions below. Each

patient will be positioned in an immobilization device in the treatment position on a flat table, arms up if possible. Contiguous CT slices, having 3 mm thickness through the regions harboring gross tumor and grossly enlarged lymph nodes and 8-10 mm thickness of the remaining regions are to be obtained starting from the level of the vocal cords and extending inferiorly through the entire liver volume. The GTV, CTV, and PTV and normal organs will be outlined on all appropriate CT slices. For correct planning all CTs need to cover both entire lungs, delineation of the entire esophagus, both lungs, heart and a reconstructed Lung volume with PTV subtracted to estimate Dmean (lungs-PTV). With 4DCT based simulation, the iGTV can be constructed expressing all CT slices where GTV is present during the respiratory cycle. Extrapolation to ITV is recommended before translating to PTV.

A treatment planning FDG PET/CT with 4D acquisition scan (or FDG-PET alone) with the patient in the treatment position is optional but strongly encouraged for treatment planning. In the case where the PET/CT is obtained in the treatment position, the CT from this study may be used as the planning CT scan.

Intravenous (i.v.) contrast during the planning CT is optional provided a diagnostic chest CT was done with contrast to delineate the major blood vessels. If not, i.v. contrast should be given during the planning CT. If contrast is used, the densities can be overridden, or the contrast scan must be registered to a non-contrast scan for planning purposes. Optimal immobilization is critical for this protocol. Immobilization to assure reproducibility of the set-up is necessary.

### **6.3.3. Target Volumes**

The definitions of target volumes will be in accordance with the 1993 ICRU Report #62.37.

**Definition of the GTV:** The primary tumor and clinically positive lymph nodes seen either on the planning CT ( $> 1$  cm short axis diameter) or pretreatment PET scan ( $SUV > 3$ ) will constitute the GTV. This volume(s) may be disjointed. In the event of a collapsed lobe or lung segment, the use of PET to distinguish tumor from fluid/atelectasis is encouraged.

**Definition of the CTV:** The CTV is defined to be the GTV plus a 0.5 cm to 1 cm margin as appropriate to account for microscopic tumor extension.

**Internal target volume (ITV)** consists of an internal margin added to the CTV to compensate for internal physiologic movement and variations in size, shape, and position of the CTV and includes here the envelope that encompasses the tumor motion for a complete respiratory cycle. Elective treatment of nodal areas is left up to the treating physician.

**Definition of the PTV:** Free-breathing non-ITV approach (i.e. standard CT simulation without 4DCT or fusion of inhalation and exhalation scans).

There are two components to the PTV expansion: the internal motion (IM margin) which should be at least 1 cm in the inferior-superior direction, 0.5 cm in the axial plane and an additional set-up margin (SU margin) of 0.5 cm. Thus, the total PTV includes the CTV plus a total margin of at least 1.5 cm to the superior-inferior dimensions and at least 1.0 cm in the axial plane.

For institutions not using 4DCT, the use of fluoroscopy to determine the margin for motion in the inferior-superior direction is encouraged. For institutions with gating technology, the use of respiratory gating is encouraged. For breath-hold or gating approaches, the PTV margin should be at least 1 cm in the inferior-superior direction and 0.5 cm in the axial plane. It is expected that daily imaging will be used for both breath-hold and gating techniques.

#### **Definition of the PTV: Free-breathing ITV approach:**

If the ITV approach is used, then the PTV margin should account for setup uncertainties and may be individualized but should not be less than 1.0 cm. If daily imaging is used in combination with motion management tools, then the margins for setup margins (iGTV to PTV) may be reduced to 0.5 cm.

In summary, there are 2 components to the PTV expansion: the internal motion (IM margin) which should be at least 1 cm in the inferior-superior direction, 0.5 cm in the axial plane and an additional set-up margin (SU margin) of 0.5 cm. Thus, the total PTV includes the CTV plus a total margin of at least 1.5 cm to the superior-inferior dimensions and at least 1.0 cm in the axial plane. In cases in which the PTV expansion extends outside of the skin, towards the spinal cord, or into the spinal canal, it can be assumed that tumor motion will not occur in this direction, and the PTV margin in this direction can be limited. PTV margin can be limited to 0.5 cm towards this dimension (skin or spinal canal).

Normal anatomy to be identified: The normal anatomy to be outlined on each CT image will include the lungs (right and left done separately), heart, skin, esophagus and spinal cord. The heart should be contoured from its base to apex, beginning at the CT slice where the ascending aorta originates. The esophagus should be contoured from the bottom of the cricoid to the gastroesophageal junction. The skin and spinal cord should be contoured on each CT slice.

#### **6.3.4. Treatment Planning**

3D Conformal Therapy: The PTV is to be treated with any combination of coplanar or noncoplanar 3-dimensional conformal fields shaped to deliver the specified dose while restricting the dose to the normal tissues. Field arrangements will be determined by 3D planning to produce the optimal conformal plan in accordance with volume definitions. The treatment plan used for each patient will be based on an analysis of the volumetric dose including DVH analyses of the PTV and critical normal structures. Each field is to be treated daily. In case of machine failure, the rest of fields can be treated the following day, any compensation in extra fractions is judged by the treating physician.

Intensity Modulated Radiation Therapy (IMRT): IMRT, as well as rotational arc planning (RapidArc/VMAT) are allowed. The NCI Guidelines for the Use of IMRT can be found on the RTOG home page, <http://www.rtog.org/>. Acceptable approaches include the use of abdominal compression devices, breath hold techniques or other motion management technologies.

### **6.3.5. Critical Structures**

Normal tissue constraints shall be prioritized in the following order for treatment planning:  
1=spinal cord, 2=lungs, 3=esophagus, and 4=heart.

1. Spinal Cord: The spinal cord dose limitation is the highest priority dose constraint and thus must be met irrespective of other constraints. Total “direct” plus “scatter” dose to the spinal cord must not exceed 50.5 in 2 Gy fractions (BED 100).
2. Lungs: The dose-volume constraint to the lungs is the second highest priority and must be met, except if it conflicts with the cord dose constraints. The volume of both lungs that receive more than 20 in 2 Gy fractions (the V20) should not exceed 37% of the total. Alternatively, the mean lung dose should optimally be 20 Gy. (By total lung volume we mean the total lung minus the PTV.) If either of these constraints is exceeded, several solutions can be entertained. First, one might increase the weighting of AP / PA treatments by one and reduce the obliques. This can be done if the cord dose (above), which takes precedence, is not exceeded. Second, one can reduce the CTV to the minimum range suggested above. Third, one can try to reduce the PTV by using respiratory gating techniques. If after all attempts to decrease the V20 to below 37%, the V20 value still exceeds this limit, the patient should be treated to the dose on the arm to which they were randomized.
3. Esophagus: Esophagus must be contoured from the cricoid/vocal cords to GE junction/pylorus. The mean dose (Dmean) to the esophagus is optimally kept below 30 Gy ([Martel 1999](#)). This is not an absolute requirement, but is strongly recommended unless other, more critical constraints force the situation. The V60 and V38 (% volume of esophagus exceeding 38 and 60 Gy, respectively) should be calculated for each patient.

\*\* For this trial, V60 must be > 20% and/or V38 >30% to be enrolled, and remain on this trial OR at least 5 cm of one surface of the esophagus must be in the 60 Gy isodose volume (to ensure that there is a similar, significant risk for esophagitis among the subjects).

OR

\*\*\* A patient in whom the final planning shows that the esophagus is close but less than 5 cm is covered in the 60 Gy isodose volume may be allowed on the trial while V60>20% or V38>30% at the discretion of the principal investigator after discussion with the Medical Monitor.

4. Heart: The following limits are recommended: 60 Gy to <1/3, 45 Gy to <2/3, and 40 Gy to <100% of the heart.

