### **Methodology:**

GTI-4419-203 will be an open-label, multi-center study to evaluate GC4419 administered intravenous (IV) for the reduction of radiation induced esophagitis in subjects receiving chemoradiotherapy for unresectable Stage 3 or post-operative Stage 2B NSCLC, SCLC treatable with chemoradiotherapy (AJCC 8th edition).

Subjects will receive radiation therapy, delivered in once-daily fractions, 5 days/week to a total dose of at least 60 Gy combined with chemotherapy other than gemcitabine, per investigator choice.

Subjects can be enrolled when an estimated 5cm of the esophagus is expected to be near the 60 Gy treatment volume.

In all subjects, the final plan should show that at least one surface of the esophagus is included in the 60 Gy isodose volume. Making sure that the full esophagus is contoured, the dose volume histogram needs to confirm high dose exposure in the range of V38 $>30\%$  and/or V60 $>20\%$ .

Each subject will receive GC4419, 90 mg, by 60-minute IV infusion, prior to each fraction of RT. GC4419 should be administered so that RT is administered within 60 minutes of the end of the GC4419 infusion.

Toxicity by common terminology criteria for adverse events (CTCAE), and esophagitis by CTCAE criteria, will be assessed at each treatment visit and 4 weeks after completion of treatment. Opioid use, weight loss, common terminology criteria for adverse events- patient reported outcome (CTCAE-PRO) fields will be assessed weekly during treatment and 4 weeks after completion of treatment. Patient-reported swallowing diaries will be completed daily. To assess early pneumonitis, NCI-CTCAE scale, CT scan, spirometry, and diffusing capacity of the lungs for carbon monoxide (DLCO) will be assessed at the end of treatment and 90 days after completion of treatment.

PK sampling will be sought from all subjects.

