### **6.3.7. Compliance Criteria**

1. Variation Acceptable: Deviations of this magnitude are not desirable but are acceptable for treatment situations in which the target to critical structure geometry is challenging. The prescribed dose can cover as little as 90% of the PTV and still be a Variation Acceptable. The minimum dose within the PTV can fall to 93% of the prescribed dose. The max dose can exceed 120% of the prescribed dose, but it cannot go above 125% of that dose. The 5 cm esophageal exposure up to 60 Gy is a pre-planning estimate for risk, final planning acceptance is judged upon V60, V38.
2. Deviation Unacceptable: Dose distributions falling in this region are not acceptable, and plan modifications should be attempted to improve results. A Deviation Unacceptable occurs if any of the Variation Acceptable dose limits stated above are exceeded. Additionally, a Deviation Unacceptable is assigned if more than 1 cm of tissue outside the PTV receives  $\geq 120\%$  of the prescribed dose.

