### 7.1. Subject Inclusion Criteria

Subjects are required to meet the following inclusion criteria before entering the trial:

1. Subjects scheduled to be treated with (definitive or adjuvant) radiation therapy in combination with chemotherapy once daily for pathologically-confirmed Stage 3 or post-operative Stage 2B NSCLC or limited stage SCLC
2. Treatment plan for subjects show that 5 cm of the esophagus for at least one surface, is included in the 60 Gy isodose volume. Dose volume histograms show esophagus dose exposure meet V38>30% and/or V60>20% (to ensure that there is a similar, significant risk for esophagitis among the subjects).

Note: In case the final planning shows that the contoured esophagus is close to but the 60 Gy isodose does not cover completely 5 cm, this subject may be allowed on the trial at the discretion of the principal investigator after discussion with and review by the Medical Monitor.

3. Age  $\geq$  18 years or older
4. ECOG performance status  $\leq$  2
5. Adequate hematologic function as indicated by:
  - a Absolute neutrophil counts (ANC)  $\geq$  1,500/mm^3
  - b Hemoglobin (Hgb)  $\geq$  9.0 g/dL
  - c Platelet count  $\geq$  100,000/mm^3
6. Adequate renal and liver function as indicated by:
  - a Estimated baseline creatinine clearance  $>60$  cc/min ( $CrCl = (140 - Age) \times Mass (kg) \times [0.85 \text{ if female}] / 72 \times [Serum Creatinine (mg/dL)]$ )
  - b Total bilirubin  $\leq$  1.5 x upper normal limit (ULN)
  - c Aspartate aminotransferase (AST) and alanine aminotransferase (ALT)  $\leq$  2.5 x ULN
  - d Alkaline phosphatase  $\leq$  2.5 x ULN
7. Males and females must agree to use a highly effective contraception starting at least one day prior to the first day of treatment and continuing for 30 days after the last dose of GC4419 (females) or 90 days (males)
8. Properly obtained written informed consent

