## **10.2. Radiation Therapy Quality Assurance**

Quality assurance for RT (RTQA) will be conducted by a prospective review of the overall treatment plan, at the time of subject screening, by a radiation oncologist who is not an Investigator on the study. For validation, RT treatment details, dosimetry, and dose volume histograms will be collected after simulation. Table position, slice thickness should be displayed on treatment plan images. For each subject, each sites' dosimetrist will calculate and document numeric information on the RTQA worksheet which will be sent for review. Recommendations, including key points for Radiation Oncologist when completing RT planning can be found in [Section 6.3](#).

It is important that CT simulation imaging is done from vocal cords (superiorly) to mid liver (inferiorly) for scan completeness covering whole esophagus and both entire lungs. 4D and/or PET fusion and acquisition is recommended for ITV, iGTV definition. For contouring, the lower border of the cricoid defines as superior extent of cervical esophagus and the GE junction/pylorus as the lower extent of esophagus.

The following data is required:

- For the esophagus: V60, V20, V38, Dmean, Dmax
- For the lung: Mean lung dose, V20 and V30

Available information should be collected regarding PTV coverage, prescribed doses for elective and gross tumor volumes, fractionation and type of chemotherapy.

This review is to confirm that the RT plan meets the eligibility requirements for the study.

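### Section 6.3.5 joins the V60/V38 thresholds and the 5 cm criterion by OR, so it admits plans that inclusion criterion 2 in Section 7.1 excludes

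*Combined protocol and SAP*

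**What the plan says.** Four places bear on which radiotherapy plans qualify.

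- **Section 7.1, criterion 2 (repeated in the synopsis).** There are two requirements in sequence. First: "Treatment plan for subjects show that 5 cm of the esophagus for at least one surface, is included in the 60 Gy isodose volume". Second: "Dose volume histograms show esophagus dose exposure meet V38>30% and/or V60>20" percent. The note allows discretion, with Medical Monitor review, only for a plan that comes close to 5 cm without fully covering it. No waiver of V60/V38 is given.
- **Section 6.3.5, item 3.** The rule here is "V60 must be > 20% and/or V38 >30% to be enrolled, and remain on this trial OR at least 5 cm of one surface" in the 60 Gy isodose volume. A further limb says that a plan close to but under 5 cm "may be allowed on the trial while V60>20% or V38>30% at the discretion of the principal investigator after discussion with the Medical Monitor".
- **Section 6.3.7.** The 5 cm is called a pre-planning estimate, and "final planning acceptance is judged upon V60, V38".
- **Synopsis, Methodology.** For all subjects, "the dose volume histogram needs to confirm high dose exposure in the range of" the same V38 and V60 values. Section 6.2 has similar wording.

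Section 6.3.1 adds that "eligibility and analyses are based on the starting treatment plan". Section 10.2 provides a prospective plan review at screening by a radiation oncologist who is not a study investigator: "This review is to confirm that the RT plan meets the eligibility requirements for the study".

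**The concern.** Section 6.3.5 is worded as a condition for enrolling and staying on the trial, not as planning advice, and it sets a different condition from the formal list. A site that follows it can enrol a subject whom Section 7.1 excludes. Section 13.3 counts a departure from the inclusion criteria as a major protocol deviation.

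The primary efficacy population in Section 12.3 depends on dosing, completion of radiotherapy and observed esophagitis. It has no eligibility condition, so the subject stays in the primary analysis. There is no control arm, and the result is tested against a fixed 30% (Section 12.6). Whatever changes the baseline risk of the enrolled subjects therefore bears directly on the test. Both 6.3.5 and 7.1 say that the exposure criterion is there to keep esophagitis risk similar and substantial across subjects.

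**Working it through.** **Step 1. The rules side by side.** Let A = at least 5 cm of one esophageal surface in the 60 Gy isodose, and B = V60 >20% and/or V38 >30%.

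- Section 7.1: A and B. A may be relaxed if the plan is close to 5 cm and the Medical Monitor has reviewed it.
- Section 6.3.5: B, or A, or (close to 5 cm and B, at discretion).

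| Plan | Section 6.3.5 | Section 7.1 |
|---|---|---|
| A and B | eligible | eligible |
| A, not B | eligible | ineligible, no waiver |
| B, not A | eligible outright | only if close to 5 cm and after Medical Monitor review |
| neither | ineligible | ineligible |

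The rules disagree in the two middle rows. For row 2, take 5 cm covered, V60 10% and V38 20%. Section 6.3.5 admits it; 7.1 does not, and it fails the V60/V38 acceptance in 6.3.7. In row 3, the discretionary limb of 6.3.5 is redundant, because B alone has already qualified the plan. That suggests the first OR is a drafting slip.

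**Step 2. Would it matter to the primary test?** The plan gives no figure for this point, so the following only illustrates it. Inputs from Sections 12.2 and 12.6: n = 55, null rate 30%, one-sided error 2.5%, alternative 13%.

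Exact binomial under 30%: P(X ≤ 9) = 0.0159 and P(X ≤ 10) = 0.0344. The test rejects at 9 or fewer events, with an actual error of 1.6%. Power at 13% is P(X ≤ 9) = 0.829, compatible with the stated rough 80%.

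Now suppose no drug effect, k subjects entered on 5 cm alone with risk r, and the other 55 − k at 30%. Then X = Bin(55 − k, 0.30) + Bin(k, r). Both k and r are assumptions. For k = 11 the expected incidence is (44 × 0.30 + 11 × r)/55.

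| Assumed r | Expected incidence, k = 11 | P(X ≤ 9), k = 11 | Smallest k giving more than 2.5% |
|---|---|---|---|
| 10% | 26.0% | 6.2% | 4 |
| 15% | 27.0% | 4.6% | 5 |
| 20% | 28.0% | 3.3% | 7 |
| 25% | 29.0% | 2.3% | 14 |
| 30% | 30.0% | 1.6% | none |
| one third | 30.7% | 1.2% | none |

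With k = 3 and r = 10% the error is 2.35%, still under 2.5%. The direction and size depend entirely on k and r, and the documents give neither.

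**The case against.** **Formal controls.** Section 7.1 is the eligibility list, and 13.3 allows only subjects who meet the protocol's criteria to be enrolled. Criteria are checked at screening (10.6) and again on Day 1 (10.7.1), and eligibility questions go to the Medical Monitor. The review in 10.2 receives V60 and V38 for every subject. This stands as a reason to expect few cases. It does not remove the conflict. No precedence is stated, 6.3.5 also presents itself as an enrolment rule, and 10.2 refers to eligibility requirements without naming them while sending radiation oncologists to Section 6.3 for planning guidance.

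**Softer wording elsewhere.** A reader might infer that every place outside 6.3.5 would reject a plan just under the cut-offs, say V60 18% and V38 28%. The documents do not support that. The synopsis methodology and Section 6.2 ask for exposure in the range of those values, and such a plan could arguably pass. The contradiction is clear for plans well below both thresholds, and against the strict cut-offs of criterion 2.

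**False positives.** A reader might also infer from the table that the trial's error rate is inflated. The documents do not show this. RTOG 1012 is described by a 5 cm criterion (4.1.2.2), about one third of its patients had Grade 2 or worse esophagitis, and this trial says it follows the same inclusion criteria (4.1.2.3). At that rate the error falls to 1.2%. Against this, 4.1.2.3 says that only half of those patients had modulated planning, while more than 75% are expected here. Lower risk in subjects admitted on 5 cm alone is therefore plausible but unproven.

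**Section 6.3.7.** It grades plan compliance and is not an enrolment criterion, so it is supporting evidence only.

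**Conclusion.** The enrolment rule in 6.3.5 is wrong as written: it contradicts criterion 2 of 7.1 in both directions. This follows from the text and needs no assumption about numbers. The practical reach is probably small, because the plan review and two eligibility checks should catch most cases. Any subject who does get through stays in the primary analysis.

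The effect on the false-positive rate is unknown. It would pass 2.5% only if the affected subjects had a lower untreated risk than 30% and there were enough of them: at least 4 at an assumed risk of 10%, or 14 at 25%. At 30% or above there is no inflation. The correction is worth making because the text is inconsistent and cheap to repair, not because bias has been demonstrated.

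**What to change.** 1. **Section 6.3.5, item 3:** replace the first OR, between V60/V38 and the 5 cm, with AND. Keep one exception only: a plan close to 5 cm that meets V60 >20% and/or V38 >30%, after Medical Monitor review, as in the note to criterion 2.
2. **Section 10.2:** state that the plan review is against criterion 2 of Section 7.1.
3. **Optional, Section 12.3 or the separate SAP:** a sensitivity analysis of the primary endpoint limited to subjects whose starting plan meets V60 >20% and/or V38 >30%.

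The cost is two wording changes and, if adopted, one analysis on values that 6.3.6 and 10.2 already require. There may be a few more screen failures; the number cannot be estimated from the documents. Those failing on V60/V38 are already ineligible under 7.1.
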